In one retrospective study of 102 adult patients at a university hospital site who were either removed from the waiting list for liver transplant or were declined transplant, patients experienced significant symptoms including pain (65% of patients), nausea (58%), lack of appetite (49%), dyspnea (48%), anxiety (36%), and depression (10%). However, only 11% of patients were referred for palliative care, and only 28% had do-not-resuscitate status in their chart.⁶ Another study considered all patients discussed by an institution's Liver Transplant Committee at a tertiary care academical medical center with a large liver transplantation program. Of 769 patients discussed, 135 were removed from transplant consideration; and only 27 of those 135 were referred to palliative care.⁷ Palliative care is often disregarded until hope of liver transplantation is lost, which may be in the last week or two of life. We hypothesize that prompting the consideration of palliative care services earlier and more consistently in context with disease-directed therapies will improve palliative care introduction into ESLD patient treatment plans subsequently yielding the hospital-free days in this population and will delay or reduce hospital readmissions while maintaining or improving quantitative and qualitative measures of quality of life and end of life care.⁸

There is potential benefit to introducing palliative care earlier in the course of illness for patients with chronic liver disease. For some patients with cirrhosis, palliative care has been shown to improve physical and emotional symptoms. In a recent observational study, Baumann et al. found that for patients with ESLD on the waiting list for liver transplant, an early palliative care intervention counteracted the progression of worsening symptoms and significantly improved pruritus, appetite, anxiety, depression, fatigue, and well-being. Moreover, the introduction of palliative care within the care course of patients with decompensated cirrhosis is endorsed by an AASLD (American Association for the Study of Liver Diseases) practice guidance document.

Full Study Title: Pragmatic Trial Investigating Surprise Question in End of Life (SeQuEL) Care and the Effect of Prompting Palliative Care Consultation on Provider Referral Rates and Subsequent Outcomes

for Hospitalized Adults with Serious Illnesses

Primary Investigator: [name], FACP, FAAHPM

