ESLD has been recognized as a condition in which early palliative care may be beneficial. ^{9,13} Patients with ESLD have high rates of severe symptoms, high levels of healthcare utilization, and a low rate of advance care planning. ^{6,8} Moreover, for patients with decompensated cirrhosis, liver transplantation is the only cure. As of March 19, 2019, over 13,000 candidates were registered on the waiting list for liver transplant in the US. ¹⁴ Previous studies in ESLD patients have shown associations of palliative care interventions with improvements in symptom control, mood, and quality of life and reduction in healthcare utilization. ^{9,13} These results suggest that the many patients who are not candidates for transplantation and those on the waitlist who may have considerable wait time would likely benefit from specialist palliative care.

We previously designed and implemented a randomized, controlled trial of a specialist palliative care intervention for ESLD patients admitted as inpatients to our institution. An important component of eligibility related to the use of the Surprise Question, which was demonstrated to be a potentially useful screening tool in this population. Due to slower than expected enrollment, the trial was terminated before full enrollment. Despite the trial's early closure, early palliative care intervention increased time to readmission and hospital free days compared to usual care with no effect on mortality, though our study was underpowered for the latter endpoint. These encouraging outcomes in this small trial indicate a potential signal for the effectiveness of specialty palliative care impact on time to readmission and

Full Study Title: Pragmatic Trial Investigating Surprise Question in End of Life (SeQuEL) Care and the Effect of Prompting Palliative Care Consultation on Provider Referral Rates and Subsequent Outcomes

for Hospitalized Adults with Serious Illnesses

Primary Investigator: [name], FACP, FAAHPM

days alive outside of the hospital in ESLD patients that should be investigated in further, fully powered studies.¹⁵

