- a. Palliative Care Consultation Prompt Group: A clinical decision support tool in the electronic health record will inform the treating clinician to consider a palliative care consultation. If the treating clinician feels a palliative care consultation would be indicated for the patient, the clinical decision support tool will facilitate the placement of a palliative care consultation by the treating clinician. If the treating clinician feels that a palliative care consultation would not be indicated, then the clinical decision support will record a reason why a palliative care consultation is not indicated.
- b. No Palliative Care Consultation Prompt Group: The patient's treating clinician will not receive a prompt in the electronic health record to consider a palliative care consultation.

A treating clinician can choose to place or discontinue a palliative care consultation at any time, retaining full autonomy to deliver the appropriate patient care. A patient may choose to request or decline a palliative care consultation at any time, irrespective of intervention assignment.

PI: [name]

Endpoints

Primary Endpoint

Stage 1: The primary outcome will be the percentage of patients with palliative care consults placed within 48 hours after enrollment. This initial stage is designed to determine feasibility and separation between groups. We are explicitly examining the separation between groups for the primary outcome at Stage 1 and have outlined the trial progression scenarios. It is anticipated that all patients will have the same data collected and will be included in the analyses for the primary, secondary, and exploratory outcomes.

Stage 2: The primary outcome will be hospital-free days by day 90. Hospital-free days will be defined as the number of calendar days between enrollment and day 90 in which the patient is alive and outside of an acute-care hospital. Days spent at home, at a rehabilitation facility, at a nursing facility, and at an inpatient hospice facility will count as hospital-free.

Secondary Endpoint(s)

There is one secondary outcome for this trial.

Survival to day 90. Defined as the number of calendar days in which the patient is alive between enrollment and day 90.

Exploratory Endpoint(s)

There are multiple prespecified exploratory outcomes for this trial.

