Total number of days in the hospital by day 90. Defined as the number of calendar days in which the patient spends at VUMC or a THA hospital between enrollment and day 90. Days spent at home, at a rehabilitation facility, at a nursing facility, and at an inpatient hospice facility will not count towards this measure.

Total number of hospital admissions by day 90. Defined as the total number of admissions at VUMC or a THA hospital that occur for the patient between enrollment and day 90.

Intensive care unit admission by day 90. Defined as any intensive care unit admission that occurs at VUMC for the patient between enrollment and day 90.

Total number of days in the intensive care unit by day 90. Defined as the total number of calendar days in which the patient stays within an intensive care unit at VUMC between enrollment and day 90.

Referral to hospice by day 90. Defined as any patient referral to inpatient or outpatient hospice that occurs between enrollment and day 90.

Emergency Department visits. Defined as the total number of Emergency Department visits at VUMC or a THA hospital that occur for the patient between enrollment and day 90.

Process Endpoint(s)

There are multiple prespecified process outcomes for this trial.

Receipt of palliative care consultation. Defined as date/time in which the patient receives the VUMC inpatient palliative care consultation between enrollment and day 90.

Time to receipt of palliative care consultation. Defined as the amount of time (hours/days) from when the palliative care consultation is placed by the provider to when the patient receives the VUMC inpatient palliative care consultation.

Number of visits with palliative care team. Defined as the total number of visits in which the patient meets with the VUMC inpatient and outpatient palliative care team between enrollment and day 90.

Completion of advance care planning upon admission as evidenced by POST form. Defined as the date and time in which the patient has completed a POST form.

Election of resuscitation status (Do Not Resuscitate (DNR) and/or Do Not Intubate (DNI)). Defined as the date and time in which the patient has elected a Do Not Resuscitate and/or Do Not Intubate at VUMC between enrollment and day 90.

Analysis dataset

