The analysis for the trial will use an intent-to-treat approach to answer the effectiveness question posed. That is, participants will be evaluated by treatment group as assigned regardless of what was delivered. All eligible participants will be included.

Statistical Approach

Our initial analysis will be descriptive in nature, summarizing information that characterizes the cohort and the outcomes. Then, we will proceed with inferential analysis to answer the main study question. Then, we will compare the secondary endpoints between study groups.

Descriptive Analysis

To characterize the study sample, baseline demographic and clinical data will be described overall and by group. Categorical variables will be described using frequencies and proportions, and continuous variables will be described using means and standard deviations, as well as medians and interquartile ranges. Missingness will be reported for each variable. Graphical summaries using extended box plots, violin plots, cumulative distribution plots, and/or histograms may be used to describe the data graphically. At a minimum, the following variables will be described at time of enrollment:

- Age (years)
- Sex (male, female, unknown)
- Race (African American, Asian/Pacific Islander, Caucasian, Multiple, Native American, Other, Unknown)
- Ethnicity (Hispanic, Non-Hispanic, Unknown)
- Comorbidities (Charlson or Elixhauser)
- MELD score

PI: [name]

We will describe all of the outcome variables overall and grouped by study arm using the same approach as for the demographic data. Summary statistics and graphical representations may be displayed, and missingness will be reported for each variable.

No statistical comparisons between groups will be done for this descriptive analysis. Please note, showing descriptive statistics stratified by treatment groups that were randomized can be easily misinterpreted, as all apparent imbalances are by definition due to chance. Descriptive statistics of all-comers need to be emphasized in randomized studies.

Main Analysis

As indicated above, the Stage 1 outcome will evaluate the proportion of patients with palliative care consults placed within 48 hours after enrollment, for an anticipated 10% of the total sample size. This initial stage is designed to determine feasibility and separation between groups. The following separations between groups, during Stage 1, would then determine trial progression to Stage 2.

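### Do the exploratory admission and ED-visit totals need a companion rate that accounts for time alive?

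*SAP*

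**What the plan says.** SAP, Exploratory Endpoint(s), gives the admissions measure as: "Defined as the total number of admissions at VUMC or a THA hospital that occur for the patient between enrollment and day 90". The ED measure is the "total number of Emergency Department visits at VUMC or a THA hospital that occur for the patient between enrollment and day 90". Hospital days and ICU days by day 90 are also plain totals. No exploratory outcome has a denominator of time alive, a rule for patients who die, or a named test.

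Three other parts of the SAP bear on how these totals will be read.

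- **Primary Endpoint, Stage 2.** Hospital-free days require the patient to be alive and outside an acute-care hospital. On where those days may be spent: "Days spent at home, at a rehabilitation facility, at a nursing facility, and at an inpatient hospice facility will count as hospital-free".
- **Secondary Endpoint(s).** Survival to day 90 is the single secondary outcome: "Defined as the number of calendar days in which the patient is alive between enrollment and day 90". Main Analysis compares it between arms with a Cox model.
- **Descriptive Analysis.** "We will describe all of the outcome variables overall and grouped by study arm", and at that step "No statistical comparisons between groups will be done for this descriptive analysis".

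The Protocol, Appendix A, 2.0 Background, expects that prompting palliative care earlier "will delay or reduce hospital readmissions while maintaining or improving quantitative and qualitative measures of quality of life". The same section says the pilot improved time to readmission and hospital-free days "with no effect on mortality, though our study was underpowered for the latter endpoint".

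**The concern.** Patients are already inpatients when enrolled. Someone who dies before discharge has no opportunity for a later admission or ED visit and scores 0 on both counts. A patient who survives 90 days and never returns also scores 0. The worst and one of the best clinical courses get the same value, and that value reads as success.

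This is harmless when the arms have equal mortality. Otherwise the arm with more early deaths has fewer patients able to return, and its mean count falls without any change in what happens after discharge. Mortality is expected to be high because of how patients are selected, and the pilot could not exclude a difference. Appendix A's background expects fewer readmissions, so a reader could take a lower raw count as support for that. The risk is a misread exploratory table; no primary or secondary conclusion depends on it.

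**Working it through.** The plan states no figure for these outcomes, so there is none to reproduce. The check has two parts: how large the shift could be, and whether a rate would improve on the raw total.

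**Inputs.** From the SAP: 388 patients per group and a reference mean of 56 hospital-free days, with 63 as the target. Assumed, because the documents give nothing: index-stay mortality; one later admission per patient discharged alive (which also sets the mean near 1); SD 1.0 to 1.5; an identical course after discharge in both arms.

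**1. Shift in the raw counts.** The ratio of means equals the ratio of proportions discharged alive.

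- 15% vs 20%: 0.80/0.85 = 0.941, a fall of 5.9%. In reverse, 0.85/0.80 = 1.0625.
- This assumes the index admission is not counted, which is the literal reading. If it is counted, the tie remains but the admissions shift is (1 + 0.80)/(1 + 0.85) = 1.80/1.85 = 0.973, a fall of 2.7%.
- The primary outcome moves the other way. Those discharged alive average 56/0.85 = 65.9 hospital-free days, so the higher-mortality arm averages 0.80 × 65.9 = 52.7.

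**2. Size against noise.** The standard error of a log ratio of means is CV × √(2/388), which is 0.072 for CV 1.0 and 0.108 for CV 1.5. A 95% interval around a ratio of 1 is then 0.87 to 1.15, or 0.81 to 1.24. The mortality gap is set against its own standard error, √{[p₁(1−p₁) + p₂(1−p₂)]/388}.

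| Assumed index-stay death | Raw ratio | Size of log ratio | Shift in SEs (CV 1.5 to 1.0) | Mortality gap in SEs |
|---|---|---|---|---|
| 10% vs 15% | 0.944 | 0.057 | 0.53 to 0.80 | 0.05/0.0237 = 2.1 |
| 15% vs 20% | 0.941 | 0.061 | 0.56 to 0.84 | 0.05/0.0272 = 1.8 |
| 10% vs 20% | 0.889 | 0.118 | 1.09 to 1.64 | 0.10/0.0254 = 3.9 |
| 15% vs 25% | 0.882 | 0.125 | 1.16 to 1.74 | 0.10/0.0285 = 3.5 |

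In every row the mortality difference is easier to see than the shift it causes in the counts.

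**3. Would a rate per day alive help admissions and ED visits?** Let D be mean days alive for those discharged and L days alive for index-stay deaths. For 15% vs 20% the ratio of rates is [0.80/(0.80D + 0.20L)] / [0.85/(0.85D + 0.15L)].

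- D = 90, L = 5: 0.996.
- D = 90, L = 15: 0.988.
- D = 75, L = 15: 0.986.

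Most of the 5.9% goes, leaving 0.4% to 1.4%. It helps less if the patients spared death are frailer. Suppose one arm has 20% mortality and the other 15%, and the extra 5% alive have twice the admissions. The raw ratio is (0.80 + 0.10)/0.80 = 1.125. With L = 10, D = 90 for the others and 60 to 90 days alive for those spared, the rate ratio is still 1.088 to 1.067.

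**4. Would it help hospital days?** Let Hs be hospital days for those discharged alive, with D = 90. The value 24.1 is 90 − 65.9. Arm means are 0.85Hs + 0.15L and 0.80Hs + 0.20L; each is divided by that arm's mean days alive to give the rate.

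| L | Hs | Raw change | Change in rate per day alive |
|---|---|---|---|
| 5 | 24.1 | −4.5% | +1.1% |
| 15 | 24.1 | −2.0% | +2.9% |
| 5 | 10 | −2.7% | +3.0% |
| 10 | 10 | 0.0% | +5.4% |
| 15 | 10 | +2.3% | +7.4% |

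For L = 10, Hs = 10, both arms average 10 hospital days; mean days alive are 78 and 74, and 78/74 = 1.054. Patients who die in the index stay spend all their days alive in hospital, so the rate rises with mortality even when care after discharge is identical. In four of the five cases it is further from no difference than the raw total. ICU days were not examined.

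**5. Days alive and out of hospital as denominator.** This removes the residual in step 3 but overlaps the primary outcome. If hospital-free days rise from 56 to 63 with admissions and deaths unchanged, the rate falls to 56/63 = 0.889. That 11.1% drop exceeds the 5.9% it was meant to correct.

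**The case for a change.** The best argument for adding the rate is that it is cheap and better fixed in advance than chosen after mortality by arm is known. Days alive is already collected, so the cost is a few sentences and a small table. The SAP itself warns that descriptive figures split by randomised arm are easily misread, and here the misreading would favour the arm with more deaths. The primary outcome accounts for death and these counts do not.

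The tie is real, the direction of the shift is right, and for admissions and ED visits a by-arm rate does remove most of it. What does not follow is that the plan is deficient without it. A total per randomised patient answers a legitimate question about burden and needs no conditioning on survival. The rate answers a different question, conditions on something that happens after randomisation, and needs a confidence-interval method for overdispersed counts. The caution against reading a lower count as benefit without looking at survival concerns interpretation, and the survival result will be in the same report. The link to a trial hypothesis is also thin: the formal aim and hypothesis (Master Protocol, section 3, which Appendix A adopts) concern consults placed and hospital-free days.

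**Conclusion.** No change is needed. The observation about the counts is correct, but it describes a property of a valid exploratory summary. Under a 5-point gap in index-stay mortality the counts move by about 6%, well under one standard error; under a 10-point gap they move by 11% to 12%, still under two. A gap of that size would itself stand out at 3.5 to 3.9 standard errors. Conclusions about benefit rest on the primary outcome and the survival comparison, both of which register death directly.

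These sizes depend on assumed mortality, one later admission per patient discharged alive, an SD of 1.0 to 1.5, the index admission not being counted, and the same course after discharge in both arms. If the analysts choose to show a by-arm rate per day alive for admissions and ED visits beside 90-day mortality, that is sensible and within their discretion. The case does not extend to hospital days, where the rate can increase the distortion, or to ICU days, which were not checked.

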- > 50% group separation: the trial would move forward to Stage 2 without modification.
- 15-50% group separation: the trial would move forward to Stage 2 with modification to the eligibility criteria, intervention, or other aspects of the study protocol.
- < 15% group separation: the trial would not move forward to Stage 2.

We are explicitly examining the separation between groups for the primary outcome at Stage 1 and have outlined the trial progression scenarios. It is anticipated that all patients will have the same data collected and will be included in the analyses for the primary, secondary, and exploratory outcomes. The main analysis of the primary outcomes will be intention to treat comparisons between patients randomized to each of the two trial groups. For the second stage primary analysis, the likelihood ratio test from the proportional odds ordinal logistic regression model will be used to compare groups on the number of hospital-free days alive. This is a generalization of the Wilcoxon two-sample test and will be adjusted for the pre-specified baseline covariates. If a baseline covariate is missing on 5 or fewer patients, it will be imputed using the grand median (mode if categorical). If any covariates are missing on more than 5 patients, multiple imputation will be used to impute sometimes-missing covariates, and the results from the separate completed-dataset analyses will be combined using Rubin's rule.

We do not expect missingness in the outcome variables.

The main analysis of the secondary outcome (survival to day 90) will be an intention-to-treat comparison between the two trial groups using a Cox Proportional-Hazards model.

There may be missingness in secondary or implementation outcomes. The cohort for which the outcome is available will be described, along with the results of the model evaluating treatment effects in this cohort. All model results will be summarized with point estimates and 95% confidence intervals (CIs), which will be emphasized over p-values when reporting the results for secondary and implementation outcomes. No adjustments for multiplicity will be made.

Additionally, a descriptive analysis of missingness tendencies is warranted. For example, logistic regression to predict the probability of missingness of an outcome measurement with predictors that include baseline variables and other outcomes that are never missing.

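### Time to receipt of palliative care consultation is timed from the consult order, not from enrollment, so it cannot show whether the prompt brings consultation earlier

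*SAP*

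**What the plan says.** Protocol section 10.4 and the Master Protocol Summary list time to receipt of palliative care consultation by name, with no time origin. The end-stage liver disease appendix defers to the Master Protocol. The SAP's Process Endpoint(s) section therefore supplies the only operational definition: "Defined as the amount of time (hours/days) from when the palliative care consultation is placed by the provider to when the patient receives" the inpatient consultation at the study hospital.

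On the intervention, the SAP says that when the clinician thinks a consult is indicated, "the clinical decision support tool will facilitate the placement of a palliative care consultation by the treating clinician". Protocol section 8.1 describes the same step.

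Two other endpoints are tied to enrollment:

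- The Stage 1 primary outcome is the "percentage of patients with palliative care consults placed within 48 hours after enrollment".
- The process endpoint on receipt of consultation is "Defined as date/time in which the patient receives the VUMC inpatient palliative care consultation between enrollment and day 90".

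On analysis, the SAP's Descriptive Analysis section says: "We will describe all of the outcome variables overall and grouped by study arm using the same approach as for the demographic data". It adds: "No statistical comparisons between groups will be done for this descriptive analysis". The Main Analysis section then says: "There may be missingness in secondary or implementation outcomes", and continues: "The cohort for which the outcome is available will be described, along with the results of the model evaluating treatment effects in this cohort". The SAP does not say which outcomes count as implementation outcomes.

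**The concern.** Earlier consultation is one of the trial's stated purposes. The protocol's Background wants palliative care introduced sooner, section 3 frames the hypothesis around prompting earlier consultation, and section 11 names timeliness of referral as a possible benefit. A reader would expect an endpoint called time to receipt to answer that question.

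It cannot. The prompt works on the interval from enrollment to order, and the SAP definition leaves that interval out. If the prompt speeds up ordering and the palliative team then responds as usual, the endpoint shows no difference. If response is slower in the prompt arm, the endpoint could make that arm look worse even though its patients are seen sooner after enrollment.

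The population is a second difficulty. The endpoint has a value only where an order was placed and a consultation took place. The prompt is meant to change who falls in that group, so the group is formed after randomisation. If the Main Analysis rule for available-outcome cohorts were applied to this endpoint, the resulting model would not be a randomised comparison. The documents do not show which way any bias would run.

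**Working it through.** **Where the clock sits.** For a patient who is consulted:

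enrollment-to-receipt = (enrollment to order) + (order to receipt)

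The SAP keeps only the second term. The prompt acts on the first. Neither document describes a step by which the prompt changes what the palliative team does once an order exists. The second term is therefore mainly service response time, although refusal, cancelled orders and discharge can also affect it.

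**Inputs for an illustration.** The plan states no figure for order or response times, so there is nothing to reproduce and every input below is assumed:

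- both delays are independent and exponential, and deaths are ignored;
- median order-to-receipt time is 24 h in the control arm and 18, 24 or 36 h in the prompt arm;
- median enrollment-to-order time is 12 h (prompt) and 72 h (control), or 24 h and 48 h.

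**Formula.** With a = ln 2 / (median order time) and b = ln 2 / (median response time), the sum of the two delays has distribution function

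`F(t) = 1 - [b*exp(-a*t) - a*exp(-b*t)] / (b - a)`

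and, where a = b, `F(t) = 1 - (1 + a*t)*exp(-a*t)`. The median solves F(t) = 0.5.

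**SAP measure (order to receipt), prompt minus control.** 18 - 24 = -6 h; 24 - 24 = 0 h; 36 - 24 = +12 h. Order times play no part.

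**Enrollment to receipt, among patients who are consulted.** Differences are taken from unrounded medians.

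| Order medians (prompt, control) | Control median | Prompt response median | Prompt median | Difference |
|---|---|---|---|---|
| 12 h, 72 h | 109.9 h | 18 h | 36.0 h | -73.9 h |
| 12 h, 72 h | 109.9 h | 24 h | 42.5 h | -67.3 h |
| 12 h, 72 h | 109.9 h | 36 h | 54.9 h | -54.9 h |
| 24 h, 48 h | 85.0 h | 18 h | 50.6 h | -34.4 h |
| 24 h, 48 h | 85.0 h | 24 h | 58.1 h | -26.9 h |
| 24 h, 48 h | 85.0 h | 36 h | 72.0 h | -13.0 h |

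With a 36 h response in the prompt arm, the SAP measure makes that arm 12 h slower, while its consulted patients are seen 13.0 to 54.9 h sooner after enrollment.

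**How far the reversal depends on the inputs.** Keep the 36 h and 24 h responses but narrow the order gap. With order medians of 24 h and 36 h, both arms have an enrollment-to-receipt median of 72.0 h, a difference of 0.0 h. With 24 h and 30 h, the difference is 72.0 - 65.2 = +6.8 h, the same direction as the SAP measure. A reversal of sign therefore needs a large enough gap in ordering.

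**Simulation check.** This used 388 per arm, 2,000 runs per scenario and a Wilcoxon test among consulted patients. Assumed mean order delays were 96 to 120 h (control) and 12 to 24 h (prompt). Mean response was 18 to 24 h, equal in the two arms, and consult rates were 20 to 30% and 30 to 60%. On the SAP clock the difference in medians averaged between -0.02 and -0.09 h, and the test rejected in 5.1 to 5.6% of runs, about its nominal 5% level. From enrollment the difference averaged -64 to -68 h and the test rejected in essentially every run.

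**The case against.** The strongest reply is that timing from enrollment is largely covered elsewhere. The Stage 1 outcome measures ordering within 48 hours of enrollment in the patients randomised, which is the step the prompt acts on. The receipt endpoint records a date and time, and the SAP will describe all outcomes by arm, possibly with cumulative distribution plots. Order-to-receipt is a legitimate service measure, and beside the Stage 1 outcome it separates ordering from response. Nothing in the protocol assigns this endpoint the task of testing earlier receipt, and the primary hypothesis concerns number of consults and hospital-free days, not timing. If the prompt acts on the order, enrollment-to-order might be the closer match.

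Much of this stands, and it limits the weight of the point. It does not remove it. Stage 1 is a yes/no on orders at 48 hours and says nothing about when patients are seen. Enrollment-to-receipt can be derived from the recorded date, but the SAP plans no such analysis, and a derivation chosen after seeing the data would not be prespecified. An enrollment-to-receipt time does include service response, but it also includes the interval the prompt targets, and it is what the endpoint's name suggests.

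Two further objections are fair. The sign reversal depends on the chosen scenarios, as the working shows, and nothing in the documents suggests that response times differ by arm. The illustration also conditions on being consulted, so it is not the analysis recommended below. The conclusion relies on neither: with equal response times, the SAP measure shows nothing however much earlier orders are placed. Finally, the warning about a non-randomised comparison is conditional, because the Descriptive Analysis section promises description only and it is unclear whether the available-cohort rule reaches process endpoints.

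**Conclusion.** The concern holds. As defined, the endpoint leaves out the interval the prompt is meant to shorten and exists only in a subset formed after randomisation, so it cannot show earlier receipt after enrollment. This follows from the definition and needs no assumed figure.

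The size is unknown, because the documents give no delays. Under the assumptions above with equal response times, the SAP measure misses a difference of 26.9 to 67.3 h in median enrollment-to-receipt time among consulted patients.

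The consequence is limited to one process endpoint. The Stage 1 progression decision, the primary hypothesis and the hospital-free-days analysis do not depend on it. The change is worth making because it costs almost nothing and lets the endpoint address a stated purpose of the trial.

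**What to change.** In the SAP's Process Endpoint(s) section, define time to receipt as the time from enrollment to the first inpatient palliative care consultation at the study hospital, in all randomised patients. Compare the arms by cumulative incidence to day 90, with death as a competing event and censoring at day 90, and report the difference with its 95% confidence interval. Do not treat discharge as a competing event, because the receipt endpoint counts a consultation at any time from enrollment to day 90.

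Keep order-to-receipt under its own name as a service-response measure. Describe it by arm, as the Descriptive Analysis section already provides, and fit no treatment-effect model to it.

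The cost is SAP wording only. Enrollment and order times are already needed for the Stage 1 outcome, receipt date and time for the receipt endpoint, and death dates for survival to day 90.
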